3 STUDY DESCRIPTION

Summary of Study Design

This will be a proof-of-concept Phase 2a study in patients with early AD. The study is designed to assess the PD, cognitive effects, PK, and safety and tolerability of obicetrapib in early AD patients. Approximately 10 to 15 patients with early AD (hetero/homozygote APO E4 carriers) will receive obicetrapib 10 mg administered orally daily for 24 weeks.

The study is intended to take place at a single site: the Brain Research Center, Amsterdam, the Netherlands. However, 1 or 2 sites in the Netherlands could be added.

The population for this study includes men and women, 50 to 75 years of age at Screening, with a clinical diagnosis of AD Stage 3 or 4 based on the National Institute on Aging-Alzheimer's Association (NIA-AA) Research Framework criteria. Patients must have an APOE genotype of E4/E4 or E3/E4.

Study duration for individual patients will approximately be 36 weeks (Screening: 1 to 8 weeks, Treatment: 24 weeks, and Follow-up: 4 weeks)

3.1.1 Screening Period

At the Screening Visit, patients and their study partners will be required to sign an informed consent form (ICF) before any study-related procedures are performed. After signing the ICF, patients will be assessed for study eligibility.

3.1.2 Treatment Period

Patients will come to the site on Day 1 (Visit 2) to begin treatment. Approximately 10 to 15 eligible patients will receive obicetrapib 10 mg once a day.

During the 24-week Treatment Period, the study drug will be administered by the patient orally and once daily on Days 1 through 168. Patients will return to the site every 6 weeks (+/- 6 days) for study assessments.

3.1.3 Safety Follow-up Period

Patients will be contacted by phone for a Safety Follow-up Visit (Visit 7) approximately 4 weeks (+/- 6 days) after the end of the Treatment Period for collection of adverse events (AEs).

Study Indication

The indication for this study is early AD.

Coronavirus Disease 2019 Contingency Measures

In cases of coronavirus disease 2019 (COVID-19) limitations, it is the Investigator's responsibility to assure the safety of patients, including phone or video contact to assess the patient's well-being including any AE, collection of study samples, and clinical data as best as possible, and direct shipment of study drug to the patient, if necessary. Where available and appropriate, home health care may be considered to facilitate monitoring of safety and study continuity. Documentation of these cases and the study site's management of patients should be recorded in the Investigator

study files. In the absence of a COVID-19 impact, it is expected that Investigators and patients follow the protocol requirements as set forth.

4 SELECTION AND WITHDRAWAL OF PATIENTS

Inclusion Criteria

Patients who meet all of the following criteria will be eligible to participate in the study:

- 1. Age range: 50-75 years of age at the Screening Visit.
- 2. Males, or females who are post-menopausal or otherwise not of child-bearing potential.
 - a. Women are not considered to be of childbearing potential if they meet 1 of the following criteria as documented by the Investigator:
 - i. They have had a hysterectomy or tubal ligation at a minimum of 1 cycle prior to signing the ICF; or
 - ii. They are postmenopausal, defined as ≥1 year since their last menstrual period for women ≥55 years of age or ≥1 year since their last menstrual period and have a follicle-stimulating hormone (FSH) level in the postmenopausal range for women <55 years of age
 - b. Men whose partners are of childbearing potential must agree to use an effective method of avoiding pregnancy from screening to 90 days after the last visit. Effective methods of avoiding pregnancy are contraceptive methods with a Pearl index of <1 used consistently and correctly (including implantable contraceptives, injectable contraceptives, oral contraceptives, transdermal contraceptives, intrauterine devices, diaphragm with spermicide, male or female condoms with spermicide, or cervical cap) or a sterile sexual partner;
- 3. Diagnosis of AD based on the NIA-AA Research Framework criteria

Biomarker classification A+T+N+ or A+T+N- based upon:

- a. CSF profile consistent with AD (an A β 42 concentration of <1000 pg/mL AND phosphorylated tau (p-Tau) >19 pg/mL, or a ratio of p-Tau/A β 42 of \geq 0.020 taken during the Screening period prior to the day of the first dose of study medication or,
- b. Documented evidence of a CSF profile consistent with AD obtained within the previous 12 months, or
- c. Documented amyloid positron emission tomography (PET) scan evidence acquired within the previous 12 months.
- 4. AD Clinical Stage 3 or 4 based on the NIA-AA Research Framework criteria
 - a. Clinical Dementia Rating scale global score ≥ 0.5 and ≤ 1
 - b. Mini-mental state examination (MMSE) score at Screening and baseline ≥ 20
- 5. Able to speak, read and write the local language fluently.
- 6. Have an APOE genotype of E4/E4 or E3/E4.

7. Patients should either be:

- a. Not treated with any approved treatments for AD with a reasonable expectation that, based on the course of illness, need for treatment is not imminent and the patient should not be initiated on treatment for the length of the study, or
- b. Stabilized on an approved medication(s) for the treatment of AD for at least 3 months prior to baseline. The dose of the AD treatment should remain the same after entering the study.
- 8. Patient and study partner are willing to consent to all study procedures.

Exclusion Criteria

Patients who meet any of the following criteria will be excluded from participation in the study:

- 1. Other than AD, neurologic or medical disorder which may impair cognition including: head trauma, seizure disorder, neurodegenerative disease, hydrocephalus, cerebral/spinal hematoma, inflammatory disease, central nervous system infection (eg, encephalitis or meningitis), neoplasm, toxic exposure, metabolic disorder (including hypoxic or hypoglycemic episodes), or endocrine disorder, or any significant medical conditions that, in the opinion of the Investigator, would prohibit their participation in the study.
- 2. Any contra-indication to undergo magnetic resonance imaging (MRI), as judged by Investigator or radiologist.
- 3. MRI of the brain indicative of significant abnormality, including, but not limited to, prior hemorrhage or infarct >1 cm³, >3 lacunar infarcts, deep white matter lesions corresponding to a Fazekas score of 3, cerebral contusion, encephalomalacia, aneurysm, vascular malformation, subdural hematoma, hydrocephalus, space-occupying lesion (eg, abscess or brain tumor such as meningioma). Small incidental meningiomas may be allowed if discussed and approved by the Principal Investigator (PI).
- 4. History of any of the following neurological, psychiatric or medical conditions:
 - a. History of large vessel stroke
 - b. History of myocardial infarction or unstable angina within the previous 12 months
 - c. Type 1 diabetes and uncontrolled type 2 diabetes (hemoglobin A1c [HbA1c] >8%)
 - d. Systemic blood pressure >150/90 mmHg on 3 separate determinations
 - e. History of hyperaldosteronism
 - f. Significant renal or hepatic dysfunction

 - e. Injected or infused antibody therapies, including but not limited antibodies directed against tumor necrosis factor (TNF), anti-interleukin(IL)-6, natalizumab, rituximab and similar agents
 - f. Anticoagulant or anti-platelet medications including warfarin, heparinoids and direct coagulation factor inhibitors (eg, apixaban, dagibatran, rivaroxaban); either aspirin at a dose of ≤100 mg/day or clopidogrel at a dose of 75 mg/day, but not both in combination is permitted.

- g. Any pharmacologic agent known to significantly induce or inhibit drug-metabolizing enzymes (especially inducers and inhibitors of CYP3A4 and CYP2C9) within 30 days before initial dosing
- h. Any lipid-altering therapies
- 9. Participation in any other interventional clinical trial, or treatment with any investigational drug or investigational use of an approved therapy within 30 days (or 5 half-lives of such agent) prior to the first Screening visit.
- 10. Regular use of cannabis or cannabis products, including non-prescription products containing cannabidiol.
- 11. History of drug (including cannabis) or alcohol abuse within the last 5 years.
- 12. Known CETP inhibitor allergy or intolerance.
- 13. Has an active severe acute respiratory syndrome coronavirus 2 (SARS-CoV-2) infection
 - a. Note: A subject being screened for this study who had a documented, positive polymerase chain reaction (PCR) or serology test for SARS-CoV-2 may be enrolled provided the subject has:
 - i. Recovered from COVID-19 ie, all COVID-19 related symptoms and major clinical findings which could potentially affect the safety of the subject should be resolved to baseline, and
 - ii. A negative result from a health authority-authorized nucleic acid amplification (PCR) test for SARS-CoV-2 taken.

Retesting

If laboratory abnormalities during Screening are considered by the Investigator to be transient, then the laboratory tests may be repeated once during Screening. The Investigator's rationale for retesting should be documented. If the retest result is no longer exclusionary, the patient may be enrolled.

Rescreening

Patients who have screen-failed are permitted to rescreen once, following consultation with the Medical Monitor. Rescreening may be scheduled after at least 5 days have elapsed from the previous study visit.

Withdrawal Criteria

Participation in this clinical study may be discontinued for any of the following reasons:

- The patient and or study partner withdraws consent or requests discontinuation from the study for any reason;
 - o However, if the patients wants to stay in the trial despite the discontinuation of the study partner, the patient is able to appoint another study partner in order to stay in the trial.
- Occurrence of any medical condition or circumstance that exposes the patient to substantial risk and/or does not allow the patient to adhere to the requirements of the protocol;

- Any SAE, clinically significant AE, severe laboratory abnormality, intercurrent illness, or other medical condition which indicates to the Investigator that continued participation is not in the best interest of the patient;
- Pregnancy;
- Requirement of prohibited concomitant medication;
- Patient failure to comply with protocol requirements or study-related procedures; or
- Termination of the study by the Sponsor or the regulatory authority.

If a patient withdraws prematurely from the study due to any of the above criteria or any other reason, study staff should make every effort to complete the full panel of assessments scheduled for the Early Termination Visit. The reason for patient withdrawal must be documented in the electronic case report form (eCRF). The patient is not obligated to undergo the full panel of assessments scheduled for the Early Termination Visit if he/she does not wish to.

In the case of patients lost to follow-up, at least 3 attempts to contact the patient must be made and documented in the patient's medical records.

Withdrawn patients will not be replaced.

5 STUDY TREATMENTS

Treatment Groups

Patients will be treated with obicetrapib 10 mg.

Rationale for Dosing

In previous multiple-dose clinical studies of obicetrapib in healthy subjects and patients, maximal effects associated with the hypothesized benefit of obicetrapib in AD patients were observed with the 10 mg obicetrapib dose. At this dose level, CETP activity and concentrations were effectively reduced, and HDL-C as well as ApoA-I and ApoE levels were maximally increased while LDL-C levels decreased.

Randomization and Blinding

Patients who meet all eligibility criteria will be enrolled into the study. All patients will be treated with obicetrapib 10 mg.

Breaking the Blind

Not applicable, the study will be conducted in an open-label fashion.

Drug Supplies

5.1.1 Formulation and Packaging

The study drug will consist of 5 mg obicetrapib tablets. All products are manufactured in accordance with current European Union Good Manufacturing Practice.

Obicetrapib tablets are round, white film-coated tablets, with no identifying markings, containing 5 mg of obicetrapib calcium drug substance.

Obicetrapib tablets will be packaged into foil blisters and assembled into wallet cards. The wallet cards will be clearly labelled to indicate which blisters to use on each day. wallet cards will be assembled into kits, and each kit will provide a sufficient supply for 6 weeks of dosing. The shelf-life will be assigned based on the stability of the individual products. The kits should be stored below 25°C.

The physical, chemical, and pharmaceutical formulation properties and characteristics of the obicetrapib tablets are described in the Investigator's Brochure.

Study drug will be labelled in accordance with all applicable local regulatory requirements.

5.1.2 Study Drug Preparation and Dispensing

The study drug used in this study will consist of 5 mg obicetrapib tablets.

At each appropriate visit (Visits 2, 3, 4, and 5), patients will receive a kit containing wallet cards with the study drug. Patients will be instructed to take 2 tablets from the wallet cards in the kit each day. The wallet cards will be clearly labelled to indicate which blisters to use on each day.

Each kit will provide a sufficient supply for 6 weeks of dosing. Patients will be instructed to return all used and unused study drug at the next visit.

This study protocol includes contingency measures to manage disruptions due to COVID-19 control measures, including modifications to study drug dispensation specific to situations where COVID-19 is impacting study conduct. See Section 3.3 for details of COVID-19 contingency measures. In the absence of a COVID-19 impact, it is expected that Investigators and patients follow the protocol requirements as set forth.

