5.1.3 Study Drug Administration

Study drug will be administered by the patient orally and once daily on Days 1 through 168. Study drug should be administered at approximately the same time each morning. If a patient forgets to take study drug on a given day, they should take the next dose as normal and should not take a double dose to make up for the forgotten dose.

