6.1.2 Visit 3 (Day 42 ± 6 Days)

All patients returning for Visit 3 (Day 42 ± 6 days) will undergo the following procedures:

- Fasting (~10 hours) blood sampling for clinical chemistry and hematology;
- Recording of vital signs;
- Administration of the Columbia-Suicide Severity Rating Scale (C-SSRS);
- Documentation of AEs and concomitant medications;
- Study drug compliance check; and

Patients will receive a supply of study drug with instructions on how to take it. Patients will be given an appointment to return with all used and unused study drug at Day 84 (± 6 days).

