6.1.4 Visit 5 (Day 126 ± 6 Days)

All patients returning for Visit 5 (Day 126 ± 6 days) will undergo the following procedures:

- Fasting (~10 hours) blood sampling for clinical chemistry and hematology;
- Recording of vital signs;
- Administration of the Columbia-Suicide Severity Rating Scale (C-SSRS);
- Documentation of AEs and concomitant medications;
- Study drug compliance check; and

Patients will receive a supply of study drug with instructions on how to take it. Patients will be given an appointment to return with all used and unused study drug at Day 168 (± 6 days).

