The cognitive component includes seven existing cognitive tests that are administered by a trained rater (duration: 20-25 minutes). The A-IADL-Q-SV measures 30 cognitively complex instrumental activities of daily living, and is completed independently by the study partner on a tablet computer (duration: 10-15 minutes). The seven existing cognitive tests include the Alzheimer's Disease Assessment Scale-Cognitive (ADAS-Cog) Word Recognition, the

ADAS-Cog Orientation, the ADAS-Cog Word Recall, the Digit Span Backward Task, the Controlled Oral Word Association Test, the Category Fluency Test, and the Digit Symbol Substitution Test.

Mini-Mental State Examination

At Screening (Visit 1), Baseline (Visit 2), Day 84 (Visit 4), and the End of Treatment (Day 168, Visit 6), the MMSE will be administered.

The MMSE is a cognitive screening test originally designed for the grading of dementia severity. The MMSE test can be performed in approximately 5 to 10 minutes. The MMSE assesses different aspects of cognition: orientation, registration, attention and calculation, recall, language, repetition, and complex commands.

MMSE scores range from 0 to 30, with a score of 24 or higher indicating normal cognition.

Exploratory Pharmacokinetic Endpoint

Mean Plasma Levels of Obicetrapib at Steady State in CSF and Plasma

At Screening obicetrapib concentrations will be measured in the CSF. At Day 1 (Visit 2) obicetrapib concentrations will be measured in plasma. At Day 84 (Visit 4) and the End of Treatment (Day 168, Visit 6), obicetrapib concentrations will be measured in the CSF and plasma samples.

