- 2. Height and weight will be measured at the Screening Visit and will be used to calculate body mass index. Weight only will be measured at the EOT visit. Measurement of weight should be performed with the patient dressed in indoor clothing, with shoes removed, and bladder empty.
- 3. Vital signs will include body temperature, heart rate, and triplicate blood pressure (systolic and diastolic) measurements.
- 4. A single, standard 12-lead ECG will be performed by the Investigator or trained site personnel at the Screening Visit and at the EOT visit.
- 5. FSH test and urine pregnancy test will be performed in women <55 years of age
- 6. Only clinical chemistry panel to be performed (Appendix B)
- 7. Clinical chemistry and part of hematology (PT, PTT, INR and platelets) only (Appendix B)
- 8. Study drug will be administered by the patient orally and once daily on Days 1 through 168. Study drug should be administered at approximately the same time each morning.
- 9. Early Termination Visit only for patients who withdraw prematurely from the study.
- 10. Optional lumbar punction.
- 11. MRI is to be performed only in patients without historical MRI available within 6 months of the Screening Visit.
- 12. A single trough PK sample will be drawn on Day 84 and 168 prior to dose to measure trough levels of obicetrapib

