3.4.1 Primary pharmacodynamic endpoints

Goal analysis: analyze change from baseline (V2; day 1) in levels of ApoA1, ApoE, and small HDL particles, in both CSF and plasma and ABCA1-driven cholesterol efflux in CSF at EOT (V6; day 168)

Variables:

- CSF and plasma ApoA1
- CSF and plasma ApoE
- CSF and plasma small HDL particles
- CSF ABCA1-driven cholesterol efflux

Methods: A Wilcoxon signed rank test will be used. We will be testing the difference between V2 (day 1; baseline) for plasma or V1 (Screening) for CSF and V6 (EOT; 168 days). Significant if p < 0.05. No multiple testing correction will be performed due to the highly correlative nature of the variables and explorative nature of the trial.

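### The Visit 6 window runs past the stated last dose, and the stated kit supply may not cover the visit windows, so in-window PD and trough samples can be taken off drug without any flag

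*Protocol*

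**What the plan says.** Protocol 5.1.3 sets the dosing period: "Study drug will be administered by the patient orally and once daily on Days 1 through 168". The Synopsis, 3.1.2, Appendix A footnote 8 and SAP 2.2.1 repeat it. Protocol 6.1.4 schedules the last on-treatment interval: "Patients will be given an appointment to return with all used and unused study drug at Day 168 (± 6 days"). Visit 6 supplies the primary PD samples in plasma and CSF (Protocol 6.1.5 and 7). It also supplies a trough PK sample, under Appendix A footnote 12: "A single trough PK sample will be drawn on Day 84 and 168 prior to dose to measure trough levels of obicetrapib". The PK endpoint in Protocol 7 is headed "Mean Plasma Levels of Obicetrapib at Steady State in CSF and Plasma".

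On supply, kits are handed out at Visits 2, 3, 4 and 5. Protocol 5.1.2 states: "Each kit will provide a sufficient supply for 6 weeks of dosing. Patients will be instructed to return all used and unused study drug" when they next attend. Neither document gives a tablet count or mentions overage. Direct shipment is offered only under the COVID-19 contingency measures.

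SAP 3.4.1 compares baseline with V6, SAP 3.4.2 uses Day 84 and V6 plasma, and SAP 3.5 summarizes PK by visit and matrix. None of these sections refers to time since the last dose.

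**The concern.** A sample meant to show the drug at steady state should follow a dose taken about one day earlier. The visit windows allow later samples in two ways: the stated dosing period can end before Visit 6, and a kit can run out before the next visit. In both cases the undosed days fall immediately before sampling. The visit would still be in window, so its timing would not be a deviation, and the value would enter the summaries and tests as an on-treatment value.

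At Visit 6 the primary endpoint is exposed. With 10 to 15 patients, one such patient is 1/15 = 6.7% to 1/10 = 10% of the primary data. At Visit 4 the exposure is smaller: exploratory plasma PD and PK. CSF at that visit is optional, and SAP 3.4.2 leaves it out of the CSF comparison.

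**Working it through.** **Inputs.** Dosing Days 1 to 168 (Protocol 5.1.3). Visit windows of ±6 days: Visit 3 on Days 36–48, Visit 4 on 78–90, Visit 5 on 120–132, Visit 6 on 162–174 (Protocol 6.1.2 to 6.1.5). Four kits, each stated as 6 weeks, taken as 42 daily doses, with leftovers returned (Protocol 5.1.1 and 5.1.2). The exact 42 is an assumption, since no tablet count is given.

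**The plan's own figure.** 4 kits × 42 doses = 168 doses = 24 weeks. The nominal schedule is covered with no slack. With every visit on its target day, the Visit 4 and Visit 6 samples come 1 day after the last dose.

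**Gap 1: stop on Day 168, supply unlimited.** Days from last dose to sample = Visit 6 day − 168, for visits after Day 168.

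| Visit 6 day | 169 | 170 | 171 | 172 | 173 | 174 |
|---|---|---|---|---|---|---|
| Days since last dose | 1 | 2 | 3 | 4 | 5 | 6 |

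Days 170 to 174 exceed one day: 5 of the 13 permitted days.

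**Gap 2: exact 42-dose kits.**
- Longest in-window interval: 90 − 36 = 132 − 78 = 174 − 120 = 54 days. If the six-week spacing in Protocol 3.1.2 is counted from the previous visit, it is 42 + 6 = 48 days.
- Before Visit 4: a kit started on Day 36 ends on Day 36 + 41 = 77. With Visit 4 on Day 90, doses on Days 78–89 are missing (12), and the sample comes 13 days after the last dose.
- Before Visit 6: a kit started on Day 120 ends on Day 161. Scheduled doses on Days 162–168 are missing (7). A Day 174 sample comes 13 days after the last dose, because both gaps then act together.
- If the visit-day dose comes from the old kit, these become 11 missing, 6 missing and 12 days.
- Under the 48-day reading, at most 48 − 42 = 6 doses are missing (5 if the visit-day dose is from the old kit).

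Of the 13 × 13 = 169 permitted day pairs, at least one dose is uncovered in 78 for Visits 3/4 (66 with the old-kit convention). For Visits 5/6 it is 63 (51), counting scheduled doses only. These are lists of permitted patterns with equal weight, not rates.

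**Would existing checks catch it?** SAP 3.4 averages the four visit compliance rates and keeps patients at 80% or more. If the denominator is elapsed days (it is not stated), the worst interval scores 42/54 = 77.8%. With the other three at 100%, the mean is (100 + 77.8 + 100 + 100)/4 = 94.4%, so the patient stays in the Per-Protocol Population.

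**The case against.** The strongest reply is that Day 168 is simply the nominal day of Visit 6. Appendix A marks study drug administration in the Visit 6 column, footnote 12 expects a dose after the sample, and Protocol 6.1.6 times follow-up from Visit 6. A Visit 6 on Days 162 to 167 also makes dosing to Day 168 impossible, since all drug is returned and none is dispensed. This stands in part. The text contradicts itself, and a site could reasonably keep dosing to the visit. But the explicit dosing rule appears in several places and no sentence extends it.

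On supply, a sufficient six-week supply is a minimum and not a count. The compliance range in Protocol 5.1.4 runs to 120%, which fits spare tablets at least as well as exact packing. This stands, and is why the second gap is conditional.

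Existing records would help. Sample dates and times are recorded (Protocol 10.1.2), tablets are counted (5.1.4 and 5.1.5), and on an elapsed-day denominator the worst interval would score 0 in SAP 3.3.7. But no analysis rule uses these to identify an off-drug sample.

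A reader might infer that the primary endpoint faces a 54-day supply need. If dosing stops on Day 168, the last kit has to cover Days 120 to 168, which is 49 days. The 12 missing scheduled doses fall before Visit 4.

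**Conclusion.** The point holds in limited form, at minor to moderate severity. Followed literally, the plan allows the primary PD samples and the end-of-treatment trough to be taken 2 to 6 days after the last dose on 5 of 13 permitted Visit 6 days. This needs no assumption about packaging, only that the dosing rule is read as written. The supply gap rests on kits holding exactly 42 doses, which the documents neither state nor exclude.

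A reader might go further and conclude that kits are short, that off-drug samples will be common, or that the PD change will be understated. The documents support none of these. Overage is not described either way. Permitted patterns do not forecast attendance, and on-target visits have no gap. No half-life or rate of PD offset is given, so neither size nor direction of an effect can be derived. That also means the documents give no basis for treating a gap of several days as harmless.

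**What to change.** 1. In Protocol 5.1.3, the Synopsis, 3.1.2, Appendix A footnote 8 and SAP 2.2.1, state that daily dosing continues until the Visit 6 samples are taken. For a Day 174 visit the added doses are Days 169 to 173, so at most 5.
2. Record the last-dose date at Visits 4 and 6. In SAP 3.4.1, 3.4.2 and 3.5, flag samples taken more than about one day after the last dose, and add a sensitivity summary without them.
3. Confirm whether kit overage covers the visit window. If it does, say so in Protocol 5.1.1. Add spare doses only if it does not.
4. State that compliance is counted against days elapsed between visits. If a kit were enlarged to 54 days and compliance counted against tablets dispensed, a fully adherent 42-day interval would score 42/54 = 77.8% and miss the 80% limit.

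The cost is a short amendment, one eCRF field if it does not already exist, and up to 5 more doses for patients with a late Visit 6. Tablets are needed only if overage is absent. Covering every permitted pattern would take a first kit of 48 days and three of 54 days: 6 × 2 + 3 × 12 × 2 = 84 extra tablets per patient, or 840 to 1,260 for 10 to 15 patients. That is an upper bound and should not be committed before step 3.
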